7.2.3 Body Weight

In Part A (SAD) and Part B (MAD), body weight will be recorded AM and PM each day of the inpatient stay and once on every outpatient visit (Part B).

Body weight for each subject should be measured on the same calibrated scale in underwear, after voiding urine, before breakfast (AM) and before dinner (PM), with the exception of days where subjects are having an OGTT without having breakfast, where they will be weighed prior to the OGTT.

At each timepoint the weight will be measured in triplicate and the mean calculated. The weight should be measured in kg to one decimal place.

7.2.4 Fluid Intake/Output

In Part A (SAD) and B (MAD) fluid intake will also be measured on the days when the subjects are undergoing food intake studies as per the Study Schedules.

7.2.5 Immunogenicity

For assessment of immunogenicity, plain tube serum samples (6 mL blood volume) will be collected prior to the first dose and at the final follow-up visit for SAD Cohort 1 and the MAD study, as subjects will be receiving multiple doses of the same peptide in these studies. Samples will be analysed using a GLP compliant and validated assay method utilising an ELISA (bridging assay format) using rabbit positive control antibodies raised against Y14.

7.3 Safety Assessments

7.3.1 Adverse Events

Definitions:

Adverse Event (AE)

Any untoward medical occurrence in a patient or clinical investigation subject administered a pharmaceutical product and which does not necessarily have to have a causal relationship with this treatment.

An AE can therefore be any clinically significant sign (including an abnormal laboratory finding, for example), symptom, or disease temporally associated with the use of a medicinal product, whether or not considered related to the medicinal product.

CONFIDENTIAL

Synoptic Clinical Study Protocol
Version 2.0 - 05/08/2017

EudraCT Number: 2017-000380-33

Adverse Drug Reaction (ADR)

Any untoward and unintended response in a subject to an investigational medicinal product which is related to any dose administered to that subject.

Serious Adverse Event (SAE)

An adverse reaction is 'serious' if it:

25. Results in death;
26. Is life-threatening;
27. Requires hospitalisation or prolongation of existing hospitalisation;
28. Results in persistent or significant disability or incapacity;
29. Consists of a congenital anomaly or birth defect;
30. Is a medically important event.

Unexpected Adverse Reactions

An adverse reaction is 'unexpected' if its nature and severity are not consistent with the information about the medicinal product in question set out:

31. In the case of a product with a marketing authorisation, in the summary of product characteristics for that product;
32. In the case of any other investigational medicinal product, in the Investigator's Brochure relating to the trial in question.

7.3.2 Reporting of Adverse Events

All adverse events must be fully recorded in the adverse event book throughout the entire study period and will be transcribed into the subjects' CRF, whether or not they are considered to be drug-related. Signs and symptoms of each AE should be described in detail: onset time and date, offset time and date, description of event, severity, relationship to investigational product, action taken and outcome.

Adverse events should be followed until recovery to the normal state has been achieved. In the event of a subject not returning to the clinical unit, the outcome of this event will be recorded as lost at follow up.

Reporting of SAEs and SUSARs

SAEs occurring on this study will be reported to the Sponsor's medical representative [name] within agreed timelines. The Investigator will be requested to complete a separate SAE reporting form in addition to the information on the CRF and in the AE book.

The Medicines for Human Use (Clinical Trials) Regulations 2004 (Statutory Instrument 1031) and subsequent amendments define the following terms:

CONFIDENTIAL

Synoptic Clinical Study Protocol
Version 2.0 - 05/08/2017

EudraCT Number: 2017-000380-33

An adverse reaction is any untoward and unintended response in a subject to an investigational medicinal product which is related to any dose administered to that subject.

A suspected unexpected serious adverse reaction (SUSAR) which is fatal or life-threatening must be reported to the competent authority and ethics committee immediately (within 7 days) after the Sponsor became aware of the event. Any additional information must be reported within eight days of sending the first report.

A SUSAR which is not fatal or life-threatening must be reported to the competent authority and ethics committee as soon as possible (within 15 days) after the Sponsor becomes aware of the event.

If a clinical trial is being conducted at a trial site in a third country in addition to sites in the United Kingdom, the Sponsor of that trial shall ensure that all SUSARs occurring at that site are entered into the European database established in accordance with Article 11 of the EU Clinical Trials Directive.

As soon as practicable after the end of the reporting year, a Sponsor shall, in relation to each investigational medicinal product tested in clinical trials in the United Kingdom for which he is the Sponsor provide the licensing authority and the relevant ethics committees with -

1. A list of all the suspected serious adverse reactions which have occurred during that year in relation to:

- those trials, whether at trial sites in the United Kingdom or elsewhere;
- or any other trials relating to that product which are conducted outside the United Kingdom and for which he is the Sponsor;

including those reactions relating to any investigational medicinal product used as a placebo or as a reference in those trials; and

2. A report on the safety of the subjects of those trials.

7.3.3 Categorisation of Adverse Events

The intensity of an AE will be categorised as follows:

Mild: Mild events are those which are easily tolerated with no disruption of normal daily activity.

Moderate: Moderate events are those which cause sufficient discomfort to interfere with daily activity.

Severe: Severe events are those which incapacitate and prevent usual activity.

7.3.4 Causal Relationship Assessment

Causal relationship assessment to drug treatments is required for purposes of reporting AEs. To promote consistency, the following guidelines should be taken into considerations along

CONFIDENTIAL

with good clinical and scientific judgment when determining the relationship of drug treatments to an AE:

Definitely Related: A clinical event, including laboratory test abnormality, occurring in a plausible time relationship to the medication administration, and which cannot be explained by concurrent disease or other drugs or chemicals. The response to withdrawal of the drug should be clinically plausible.

Possibly Related: A clinical event, including laboratory test abnormality, with a reasonable time sequence to the medication administration, but which could also be explained by concurrent disease or other drugs or chemicals. Information on the drug withdrawal may be lacking or unclear.

Unlikely Related: A clinical event, including laboratory test abnormality, with little or no temporal relationship to medication administration, and which other drugs, chemicals or underlying disease provide plausible explanations.

Not Related: A clinical event, including laboratory test abnormality that has no temporal relationship to the medication or has more likely alternative aetiology.

7.3.5 Action Taken

Action taken will be defined as:

- None;
- Medication given;
- Dosing interrupted (this applies to Part B only as it involves multiple dosing);
- Dosing stopped (this applies to Part B only as it involves multiple dosing).

7.3.6 Outcome

Outcome will be defined as:

- Resolved;
- Ongoing;
- Lost to follow up.

7.3.7 Coding of Adverse Events

All adverse events will be coded using the current version of Medical Dictionary for Regulatory Activities (MedDRA).

CONFIDENTIAL

Synoptic Clinical Study Protocol
Version 2.0 - 05/08/2017

EudraCT Number: 2017-000380-33

7.4 Clinical Laboratory Safety Tests

Sample collection times are included in the schedule of events.

Additional and repeat testing may be performed at the discretion of the Principal Investigator. Safety laboratory variables to be assessed are presented in Table 7.3.

Table 7.3 Safety Laboratory Variables

Haematology	White blood cells Red blood cells Mean corpuscular volume Mean corpuscular haemoglobin Mean corpuscular haemoglobin concentration Haemoglobin	Haematocrit Neutrophils (absolute and %) Lymphocytes (absolute and %) Monocytes (absolute and %) Eosinophils (absolute and %) Basophils (absolute and %) Platelets
Biochemistry	Sodium Potassium Urea Creatinine Alkaline phosphatase Alanine aminotransferase Creatine kinase Gamma-glutamyltransferase Lactate dehydrogenase Aspartate aminotransferase Glucose Lipase Amylase	Total bilirubin Calcium Chloride Total protein Globulin Cholesterol Triglycerides Uric acid Phosphate Albumin Bicarbonate C-reactive protein ¹
Coagulation	Prothrombin time International normalized ratio	Activated partial thromboplastin time
Thyroid Function	TSH, FT4	
Biomarkers	Histamine	Tryptase
Urinalysis	Protein Bilirubin Urobilinogen Ketones Glucose	Leukocytes Red blood cells pH Nitrite Specific gravity
Urine Microscopy	Microscopic investigation of sediment in case of pathological findings [performed if clinically indicated]	
Viral Serology	HIV I and II HBsAg	Hepatitis C virus
Drugs of Abuse and Alcohol Screen	Amphetamine / Ecstasy Cannabinoids Cocaine Opiates	Benzodiazepines Methadone metabolites Barbiturates Cotinine
Alcohol Screen (Breath test)	Alcohol	

¹ At screening only

CONFIDENTIAL

Synoptic Clinical Study Protocol
Version 2.0 - 05/08/2017

EudraCT Number: 2017-000380-33

Unless otherwise specified in the schedule of assessments all clinical laboratory tests will be performed by CRO Pathology Lab, which is a GLP Accredited Laboratory. Details of all methodology and reference ranges are provided in the Trial Master File.

7.5 Clinical Safety Assessments

Assessment times are included in the schedule of events. Time points of assessments may be amended based on emerging safety, tolerability and PK data.

7.5.1 Vital Signs

Blood pressure and pulse rate will be measured using an automated instrument with the subject in the supine position after resting comfortably for 10 minutes. Body temperature will be measured orally in degrees Celsius using an automated thermometer. Additional vital signs measurements may be added for safety of the subjects.

Measurements will be reported in the subject's CRF.

7.5.2 12-Lead ECG

Computerised 12-lead ECG recordings will be obtained. after 5 minutes supine rest. Each lead shall be recorded for at least 3 beats at a speed of 25 mm/sec.

The following parameters will be recorded: ventricular rate, PR interval, QRS duration, QT and QTc.

7.5.3 Medical History

A complete medical history will include evaluation (past or present) of the following: general, head and neck, eyes, ears, nose throat, chest/respiratory, heart/cardiovascular, gastrointestinal/liver, gynaecological/urogenital, musculoskeletal/extremities, skin, neurological/psychiatric, endocrine/metabolic, haematologic/lymphatic, allergies/drug sensitivities, past surgeries, substance abuse or any other diseases or disorders.

7.5.4 Physical Examination

Physical examinations will be performed by a physician and will include the examination of the following: general appearance, eyes, ears, nose, throat, chest/respiratory, heart/cardiovascular, gastrointestinal/liver, musculoskeletal/extremities, dermatological/skin, thyroid/neck, lymph nodes, neurological/psychiatric.

7.5.5 Bedside glucose testing

Where indicated in the Study Schedules, bedside glucose testing will be carried out.

7.5.6 Local Injection Site Reactions

Injection sites will be monitored while the subject is resident in the clinical unit for redness, swelling, pain, tenderness and bruising. Reaction grades are provided in Table 7.4.

In the event that there are injection site reactions thought to be related to the volume of the injection, subsequent doses may be split into a maximum of 5 smaller injections.

CONFIDENTIAL

Synoptic Clinical Study Protocol
Version 2.0 - 05/08/2017

EudraCT Number: 2017-000380-33

Injection site reactions with a Grade ≥ 1 will be recorded as an AE.

Table 7.4 Injection Site Reaction Grading Scheme

Reaction	Grade 0	Grade 1	Grade 2	Grade 3	Grade 4
Redness ¹	0–24 mm	25–50 mm	51–100 mm	More than 100 mm	Requires medical intervention greater than analgesia
Swelling ²	0–24 mm	25–50 mm and does not interfere with activity	51–100 mm or interferes with activity	More than 100 mm and prevents daily activity	Requires medical intervention greater than analgesia
Pain	None	Does not interfere with activity	Interferes with activity or repeated use of non-narcotic pain reliever	Prevents daily activity or repeated use of narcotic pain reliever	Requires medical intervention greater than analgesia
Tenderness	None	Mild pain to touch	Moderate pain to touch	Severe pain to touch	Requires medical intervention greater than analgesia
Bruising	None	Present			
Ulceration ± tissue necrosis	None	None	None	None	Present

1 Assessed by estimating the size of the red patch at the injection site across its widest point

2 Assessed by estimating the size of the raised area around the injection site across its widest point; also take into account how much it affects the subject in their routine daily activities.

CONFIDENTIAL

Synoptic Clinical Study Protocol
Version 2.0 - 05/08/2017

EudraCT Number: 2017-000380-33

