6.2 Dosage and Administration

Y14 or placebo will be administered by SC injection into the abdomen. The maximum individual injection volume will not exceed 1.0 mL, though multiple injections (up to 5) may be given for a single dose. The injection site(s) should be circled with indelible marker (or the position recorded in some other suitable manner) and inspected at each AE check during Day 1. Reactions should be described according to the grading table (Table 7.4). Where multiple doses of Y14 are given to the volunteer, the injection sites must rotate, i.e. given at different sites in the abdomen.

In the event of injection site reactions thought to be related to the volume of the injection, the dose of Y14 or placebo may be fractionated and up to 5 injections may be given.

Subjects will receive Y14 or placebo, whilst in the supine/semi-supine position, said dose to be given 1 hour after the subject has completed eating a standardised breakfast. Subjects will remain confined to their beds for a period of 4 h after injection, but will be permitted to visit the bathroom to use the toilet if needed.

In Part A (SAD) the proposed doses are: 1 mg, 4 mg, 8 mg, 16 mg, 32 mg, 64 mg and 96 mg. Depending on emerging safety, tolerability and PK data, the doses given may be modified. Dose levels administered in Part B (MAD) will be selected following review of the data from Part A. In Part B, dose titration for an individual subject may be necessary within a dosing regimen depending on the activity profile and tolerability, but will not exceed the maximum dose tested in the SAD trial.

Subjects will not eat for 4 h postdose after which time lunch will be served. Dinner will be served 10 h postdose.

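### Two safety definitions need rewording: seriousness is defined only for drug-related reactions, and Table 7.4, read literally, gives no grade to a swelling over 100 mm that leaves activity unaffected

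*Combined protocol and SAP*

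**What the plan says.** **Seriousness.** Section 7.3.1 defines an AE without regard to causality and an adverse drug reaction as a response related to a dose. Under the SAE heading it then lists the seriousness criteria for an adverse *reaction*. Section 7.3.2 defines an adverse reaction as dose-related in the same way, and requires SAEs to be reported to the sponsor's medical representative.

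**Injection site swelling.** The swelling row of Table 7.4 (section 7.5.6) combines size and activity:
- Grade 0 is 0–24 mm.
- Grade 1 is 25–50 mm "and does not interfere with activity".
- Grade 2 is 51–100 mm "or interferes with activity".
- Grade 3 is "More than 100 mm and prevents daily activity".
- Grade 4 is a need for intervention beyond analgesia.

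Footnote 2 asks the grader to measure the raised area and "also take into account how much it affects the subject in their routine daily activities". Reactions of Grade 1 or higher "will be recorded as an AE". Section 6.2 requires reactions to be described by this table.

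**Action codes (minor).** Section 7.3.5 restricts the codes for interrupted and stopped dosing to Part B, giving multiple dosing as the reason. Section 5.1.1 doses Part A Cohort 1 in three treatment periods and, in its immunogenicity paragraph, describes those volunteers as having had multiple doses.

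**The concern.** Adverse events are among the primary target variables (section 10.1). A definition that depends on relatedness takes the serious label away from any event judged unrelated, and with it the route to the sponsor that section 7.3.2 attaches to SAEs.

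Injection site reactions matter in this programme. Section 3.2 reports that skin reactions were common with the earlier analogue and promises close monitoring of local tolerance. As worded, a larger swelling can escape a recording trigger that a smaller one meets. Nothing else in the table suggests that this was intended. Redness over 100 mm is Grade 3 on size alone ("Assessed by estimating the size of the red patch at the injection site across its widest point"), and Grade 3 pain is "Prevents daily activity or repeated use of narcotic pain reliever", with no size condition.

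**Working it through.** The plan gives no figure to reproduce here. The check is a comparison of sections and an enumeration of one table row.

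**Seriousness, sections side by side**
1. Section 7.3.1: serious applies to an adverse reaction. Sections 7.3.1 and 7.3.2: a reaction is related to a dose. Together, an SAE must be related.
2. Section 5.1.4: the halt criterion takes an SAE and then adds that it must be thought related. The rule for stopping an individual's dosing likewise qualifies a serious adverse event as possibly drug-related. Both qualifiers would be redundant if relatedness were already part of the term.
3. Section 5.2.3.4: miscarriage and congenital abnormality are reported as SAEs with no causality test.
4. Items 2 and 3 use the wider meaning and conflict with item 1. The halt criterion and SUSAR reporting require relatedness in any case, so the wording in 7.3.1 does not change them. What it changes is the classification of unrelated serious events and their reporting to the sponsor.

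**Swelling row of Table 7.4**

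Inputs: the four size bands in the table and three activity levels (no effect, interferes, prevents), with no intervention beyond analgesia. That gives 4 × 3 = 12 combinations. Grades met when 'prevents' is taken to include 'interferes':

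| Size | No effect | Interferes | Prevents |
|---|---|---|---|
| 0–24 mm | 0 | 0 and 2 | 0 and 2 |
| 25–50 mm | 1 | 2 | 2 |
| 51–100 mm | 2 | 2 | 2 |
| Over 100 mm | none | 2 | 2 and 3 |

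- No grade: 1 of 12. Two grades: 3 of 12. Without a unique grade: 1 + 3 = 4 of 12. With a single grade: 12 − 4 = 8.
- If 'prevents' and 'interferes' are taken as exclusive, 25–50 mm with activity prevented also has no grade (assuming it does not count as Grade 1), and only 0–24 mm with interference has two. That is 2 + 1 = 3 of 12 without a unique grade.
- The cell for over 100 mm with no effect on activity is empty both ways.
- Example: 80 mm with no effect is Grade 2 and must be recorded, while 101 mm with no effect meets no grade.

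**Candidate repairs**, each with 'prevents' including 'interferes' and the highest grade met applied. Rows run from the smallest size band to the largest:

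| Change | Resulting grades | Single-grade cells altered |
|---|---|---|
| Grade 2 size becomes 51 mm or more | 0,2,2 / 1,2,2 / 2,2,2 / 2,2,3 | 0 of 8 |
| Grade 3 on size over 100 mm alone | 0,2,2 / 1,2,2 / 2,2,2 / 3,3,3 | 1 of 8 (over 100 mm, interferes: 2 to 3) |
| Grade 3 'and' becomes 'or' | 0,2,3 / 1,2,3 / 2,2,3 / 3,3,3 | 3 of 8 (over 100 mm, interferes; 25–50 and 51–100 mm, prevents: each 2 to 3) |

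All three are complete and never decrease with size or activity. Putting only the empty cell into Grade 3 fails, because the last row would read 3, 2, 3.

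**The case against.** **The event need not be lost.** A reader might infer that the large swelling would go unrecorded. The documents do not support that. The AE definition in section 7.3.1 opens with any untoward occurrence and sets no significance threshold there. Section 7.3.2 requires all AEs to be recorded, and section 6.2 has the sites inspected at each AE check on Day 1. The Grade 1 rule says what must be recorded; it does not exclude the rest. This objection stands, and it limits the consequence to a missing grade and a missing objective trigger.

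**The gap depends on a literal reading.** A reader might also infer that no reading of the table grades this swelling. That is too strong. A grader who treats the size bands as ascending thresholds would say that a swelling over 100 mm has passed the Grade 2 limit, and footnote 2 leaves room for judgement. The table does not state a threshold rule, however, so two graders could differ.

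**The case is narrow.** The trigger fails only if there is also no redness of 25 mm or more, pain, tenderness, bruising or ulceration, since each of these is at least Grade 1 in its own row. No stopping rule in section 5.1.4 cites a Table 7.4 grade, and section 10.6 summarises AEs by MedDRA. The 12-cell counts weight every cell equally and say nothing about how often a cell occurs. All of this stands.

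**The action codes are close to a matter of preference.** Cohort 1 receives one dose per period and is re-randomised each time, and section 5.2.4 already provides for withdrawal before Periods 2 or 3. Only the description of Cohort 1 as having multiple doses conflicts with the reason given in section 7.3.5.

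**Conclusion.** Both wording errors are real, and correcting them is cheap.

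The SAE definition is an internal inconsistency. Taken literally, it removes the serious label, and the SAE reporting to the sponsor, from any serious event judged unrelated. Such an event would still be recorded as an AE. A reader might infer that the halt criterion or SUSAR reporting is weakened; neither is, because both require relatedness anyway.

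The table gap is narrower. On a literal reading, and with no intervention beyond analgesia, one of 12 combinations has no grade. Three more have two grades if 'prevents' includes 'interferes', and the table gives no rule for choosing between them. The documents allow no estimate of the effect on AE incidence, and none is claimed.

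The action-code wording is a minor inconsistency.

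**What to change.** 1. **Section 7.3.1:** reword the lead-in to the criteria to 'An adverse event is serious if it ...'.
2. **Table 7.4, swelling:** state that 'prevents' includes 'interferes' and that the highest grade met applies, and change the Grade 2 size to 51 mm or more. This fills the empty cell, settles the three double-graded cells and leaves all eight single-grade cells as they are. The statement about 'prevents' is needed: without it, 25–50 mm with activity prevented can still be left without a grade. If the sponsor prefers Grade 3 on size alone, or 'or' in place of 'and', it should record that some swellings now at Grade 2 move to Grade 3, and that reactions already graded may not compare with later ones.
3. **Section 7.3.5:** reconcile the Part B restriction with the description of Cohort 1 in section 5.1.1.

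The cost is wording edits in three sections and possibly one CRF option. No procedures or visits are added. If reactions have already been graded, any in the empty or double-graded cells should be checked against the new wording.
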